6.6.1. Pre-specified Patient Discontinuation rules

If a patient experiences a Grade IV Common Terminology Criteria for Adverse Event (CTCAE) or meets liver injury criteria as listed in section 6.6.3., the study drug should be interrupted. After causality assessment by the DSMB, if the AE or lab abnormality is considered unrelated to study drug, and the event has resolved or returned to baseline, then the study drug may be re-

started. If the event reoccurs after restart of study drug, then the study drug will be permanently discontinued.

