6.6.2. Pre-specified Trial Discontinuation rules

If one patient experiences a Grade V CTCAE, or 2 patients experience the same Grade IV CTCAE, or 3 patients experience the same Grade III CTCAE, or 4 patients experience the same Grade II CTCAE, the trial will be paused. The DSMB will assess causality of these adverse events; if the events are deemed unrelated to study drug, the trial will continue.

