6.6.5. Data Safety Monitoring Board

An independent Data Safety Monitoring Board (DSMB) composed of 3 liver experts will review the safety of patients enrolled in the trial. The DSMB will perform a safety data review every 3 months, the first review occurring 3 months after first patient randomized. A DSMB charter will define the role, responsibilities, rules, and tasks of the DSMB.

The DSMB will ensure that the patient and trial discontinuation rules are respected and will determine the causality assessment of the events described in sections 6.6.1, 6.6.2., and 6.6.3., in order to make the recommendation for trial /patient discontinuation. If the events are deemed unrelated to the study drug by the DSMB, then the patient or the trial will continue.

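### The trial-pause rule ties each count to one exact CTCAE grade, so read literally a mixed-grade cluster can fail to pause the trial when a milder cluster of the same size would

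*Protocol*

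**What the plan says.** Protocol 6.6.2 is the only trial-level stopping rule with stated counts. It begins "If one patient experiences a Grade V CTCAE, or 2 patients experience the same Grade IV CTCAE" and continues "3 patients experience the same Grade III CTCAE, or 4 patients experience the same Grade II CTCAE, the trial will be paused". What follows a pause is also stated: "The DSMB will assess causality of these adverse events; if the events are deemed unrelated to study drug, the trial will continue".

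Three neighbouring provisions bear on it.

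- Protocol 6.6.1 works at patient level. Its trigger reads "If a patient experiences a Grade IV Common Terminology Criteria for Adverse Event (CTCAE) or meets liver injury criteria"; that patient's drug is then interrupted and the DSMB judges causality.
- Protocol 6.6.4 sends cases meeting the liver criteria to the DSMB.
- Protocol 6.6.5 gives the board's task and timetable: "The DSMB will ensure that the patient and trial discontinuation rules are respected", and "The DSMB will perform a safety data review every 3 months, the first review occurring 3 months after first patient randomized". It leaves further rules to a separate document: "A DSMB charter will define the role, responsibilities, rules, and tasks of the DSMB".

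Neither these sections nor SAP section 4 contains the words *or higher* or *at least*, or any instruction to grade a patient by the worst value. The charter is not among the documents.

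**The concern.** The required count falls as severity rises (4, 3, 2, 1), so worse cases were plainly meant to weigh more. With each count attached to one named grade, the literal rule can do the reverse. If one of four Grade II cases is instead seen at Grade III, the Grade II limb drops to three, the Grade III limb stands at one, and neither is met. The worse cluster does not pause the trial and the milder one does.

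This matters because safety is the primary objective (Protocol 2.1), there is no control arm, and Protocol 1.3 describes the study as the first of the drug in this population. Under Protocol 6.7 the DSMB's causality assessment follows when the stopping criteria are met, so the wording of the criteria decides whether the board is called.

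**Working it through.** The plan gives no operating characteristic for the pause rule, so there is no figure to reproduce. The check has two parts.

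**1. Enumeration (no assumption about rates).** Take one event term, count each patient once at one grade, and let II, III and IV be the numbers of patients at each grade. A Grade V event pauses under either reading and is left out.

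- Literal pause: II ≥ 4, or III ≥ 3, or IV ≥ 2.
- Cumulative pause: IV ≥ 2, or III + IV ≥ 3, or II + III + IV ≥ 4.

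The literal rule stays silent when II is 0–3, III is 0–2 and IV is 0–1, which is 4 × 3 × 2 = 24 combinations. Ten of these pause under the cumulative rule:

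| Patients | Combinations (II, III, IV) |
|---|---|
| 3 | (0,2,1) |
| 4 | (1,2,1), (2,1,1), (2,2,0), (3,0,1), (3,1,0) |
| 5 | (2,2,1), (3,1,1), (3,2,0) |
| 6 | (3,2,1) |

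Each has a milder cluster of equal size that does pause literally: three Grade III for (0,2,1), and all Grade II for the other nine. The largest silent cluster is 6 of 20 patients (30%); under the cumulative rule it is 3. Three of the ten contain no Grade IV case: (3,1,0), (2,2,0) and (3,2,0).

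**2. Probability of a pause (illustrative).** The number of patients, 20, comes from Protocol 4.1. The event rate and the split across grades are assumptions, because the documents give neither. With p₂, p₃, p₄ the per-patient probabilities of the event at Grades II, III and IV, and p₀ = 1 − p₂ − p₃ − p₄,

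P(a,b,c) = 20! / [a! b! c! (20−a−b−c)!] × p₂^a p₃^b p₄^c p₀^(20−a−b−c),

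summed over the combinations that pause.

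| Rate at Grade II or above | Split II/III/IV (%) | Literal | Cumulative | Gap |
|---|---|---|---|---|
| 10% | 60/30/10 | 0.066 | 0.151 | 0.09 |
| 10% | 80/18/2 | 0.076 | 0.135 | 0.06 |
| 10% | 90/10/0 | 0.100 | 0.133 | 0.03 |
| 20% | 60/30/10 | 0.355 | 0.607 | 0.25 |
| 20% | 80/18/2 | 0.426 | 0.590 | 0.16 |
| 20% | 90/10/0 | 0.502 | 0.589 | 0.09 |
| 30% | 60/30/10 | 0.704 | 0.899 | 0.20 |
| 30% | 80/18/2 | 0.777 | 0.894 | 0.12 |
| 30% | 90/10/0 | 0.836 | 0.893 | 0.06 |

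At a 5% rate the gaps are 0.005 to 0.012.

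The part of the gap that no Grade IV referral could soften comes from the three Grade II/III combinations. At 20% and 60/30/10, p₂ = 0.12, p₃ = 0.06, p₄ = 0.02 and p₀ = 0.80:

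- (3,1,0): 19,380 × 0.12³ × 0.06 × 0.80¹⁶ = 0.057
- (2,2,0): 29,070 × 0.12² × 0.06² × 0.80¹⁶ = 0.042
- (3,2,0): 155,040 × 0.12³ × 0.06² × 0.80¹⁵ = 0.034

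The sum is 0.133. For the other two splits at 20% it is 0.137 and 0.087. The largest silent cluster, (3,2,1), has probability 0.013 in the 60/30/10 case.

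**The case against.** **The literal reading is uncharitable.** The text does not say *exactly* or *worst grade*. A patient who worsens from Grade II to III has had the event at both grades, and three liver experts would probably count a worse case toward the lower limb. This is likely the intent. Counting patients at the lower grades they passed through shrinks the gap: at a 20% rate, if half of the worse cases are also counted at each lower grade, the gaps become 0.12, 0.08 and 0.04; at 80% they become 0.05, 0.03 and 0.02. But the protocol does not state this, and an event first found at Grade III at a four-weekly visit may never have been seen at Grade II.

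**The charter may settle it.** It may. The protocol text does not.

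**Other safeguards apply.** Seven of the ten combinations contain a Grade IV case, which already goes to the DSMB. Liver cases do too. Serious events are reported to the safety vendor within 24 hours (Protocol 7.3.2), unacceptable toxicity ends a patient's treatment (6.7), and the investigator may terminate the study at any time (9.13). At a single open-label site, one team sees every event. All of this reduces the practical weight, but none of it is an automatic pause for a cluster. Non-hepatic mixes of Grades II and III have no automatic referral, so the board might first see them at a 3-monthly review within a 24-week treatment period.

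**The probabilities rest on assumed rates.** They do, and Protocol 1.2.2 describes the gastrointestinal events as generally mild, which argues against the heavier mixes. The enumeration does not depend on them.

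**The change has a cost.** Causality is judged only after the pause, so unrelated events would also trigger more pauses, by up to 25 percentage points for one term in the heaviest 20% scenario. That is a fair description of the price.

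**Conclusion.** The concern holds. As written, section 6.6.2 is not ordered by severity: ten combinations of same-event cases, involving 3 to 6 of 20 patients, escape a pause that a milder cluster of equal size would trigger. That result needs only the literal reading, with each patient counted at one grade.

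The practical size is uncertain. Across the assumed rates of 5% to 30% and the three grade mixes, the loss in pause probability for one event term runs from 0.005 to 0.25, and it is smaller if patients are also counted at the grades they passed through. The residual exposure that matters most is narrow: non-hepatic Grade II/III clusters of four or five patients arising between DSMB reviews. This is a drafting gap in a key safety rule and should be closed, subject to what the unseen charter says.

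**What to change.** In section 6.6.2, keep the counts 1, 2, 3 and 4 and reword the last three limbs as: *2 patients with the same event at Grade IV or higher, 3 at Grade III or higher, or 4 at Grade II or higher, each patient counted once at the worst CTCAE grade reached for that event.* Put the same sentence in the DSMB charter. All ten combinations then pause, and the largest same-event cluster that does not falls from 6 patients to 3.

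The cost is one sentence in each document and more pauses for causality review, after which the trial continues if the events are judged unrelated. Protocol 7.2.1 records intensity only as mild, moderate or severe, but section 6.6.2 already requires CTCAE grades, so the change adds no new grading.

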6.6.3. Dose Adjustment

Enrolled subjects who experience treatment emergent adverse events should be monitored closely and may have the NTZ dose adjusted at the Principal Investigator's discretion.

Enrolled subjects who experience a possible treatment emergent adverse event will be assessed for symptoms and further biochemical assessments as follows:

- GI Adverse Events: the subject will be assessed for abdominal pain, loss of appetite, nausea and vomiting. Blood will be collected for amylase and lipase assessment to rule out pancreatitis.
- Kidney Function Adverse Events: the subject will have blood samples collected for eGFR to rule out kidney dysfunction.
- Musculoskeletal Adverse Events: the subject will be assessed for fatigue, muscle aches and pain. Blood samples will be collected for Creatine Kinase.

The following procedure will be followed for dose adjustments:

1. Patients will be asked to hold drug for 3 days
2. After the 3-day drug hold, patients will be reassessed for adverse event symptoms.
 - If the AE symptoms have resolved following 3 days of drug hold, the patient will discontinue NTZ dosing permanently and will be followed per the schedule of assessments.

If the AE symptoms have not resolved following 3 days of drug hold, the patient will be restarted on a reduced dose of 500 mg NTZ, once a day for 7 days. Patients will be evaluated for treatment emergent adverse events and consideration for resuming the dosage of 500mg NTZ twice a day. PI may determine that the patient should remain at the 500 mg NTZ once a day dose following 7 days of reduced dose. In such scenarios, the patient will be monitored and consideration for resuming the dosage of 500 mg NTZ twice daily will be evaluated at each subsequent visit.

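### Protocol 6.6.3 stops NTZ for good if symptoms clear during a 3-day hold and restarts it if they persist, without using the tests it orders; the intended direction needs confirming

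*Protocol*

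**What the plan says.** Protocol 5.6 and 6.6.3 leave it to the Principal Investigator whether to adjust the dose. Once that choice is made, 6.6.3 sets a fixed sequence: "The following procedure will be followed for dose adjustments". NTZ is held for 3 days, after which "patients will be reassessed for adverse event symptoms". There are two outcomes:

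- "If the AE symptoms have resolved following 3 days of drug hold, the patient will discontinue NTZ dosing permanently"; follow-up then continues on the normal schedule.
- "If the AE symptoms have not resolved following 3 days of drug hold, the patient will be restarted on a reduced dose", namely 500 mg once daily for 7 days. Return to twice daily is considered then or at later visits.

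The same section orders tests by type of event. For GI events, "Blood will be collected for amylase and lipase assessment to rule out pancreatitis". For kidney events, "the subject will have blood samples collected for eGFR to rule out kidney dysfunction". For musculoskeletal events, creatine kinase is drawn.

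Protocol 6.6.1 covers Grade IV events and liver injury. It lets NTZ restart only "if the AE or lab abnormality is considered unrelated to study drug, and the event has resolved or returned to baseline". Protocol 6.6.4, for liver enzyme interruptions, lets the DSMB allow a restart if it judges the event not related to the drug.

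**The concern.** Two features look wrong. The first is direction. A patient who has recovered is taken off the drug for good, and one who is still unwell is dosed again. That is the opposite use of resolution from 6.6.1.

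The second does not depend on direction. 6.6.3 orders tests to look for pancreatitis, kidney dysfunction and muscle injury, then makes the restart decision without referring to any of the results. It also attaches no causality condition to either branch.

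The main stake is patient safety: the written rule can re-expose a symptomatic patient whose laboratory result is abnormal. There is also a reporting consequence. Safety and tolerability is the primary objective, and SAP 3.5.1 counts AEs leading to withdrawal from study or study drug. Protocol 1.2.2 describes GI events on NTZ as mostly mild and short-lived. The expected event, if held, would therefore tend to fall in the permanent-stop branch, and the withdrawal count would partly reflect this rule.

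**Working it through.** The plan gives no figure on this point, so there is nothing to recompute. The check compares the rules with one another.

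**Step 1. Restart rules side by side.**

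| Protocol section | Applies to | Role of resolution | Causality condition | Laboratory result used |
|---|---|---|---|---|
| 6.6.1 | Grade IV event or liver injury | Required for restart (or back at baseline) | Unrelated, per DSMB | Yes, laboratory abnormalities are named |
| 6.6.4 | Liver enzyme interruption | Monitored until resolved or stable | Not related, per DSMB | Yes, ALT and bilirubin thresholds |
| 6.7 | Intercurrent illness | Required for restart | None stated; investigator discretion | None stated |
| 6.6.3 | Treatment-emergent AE where the dose is adjusted | Resolution leads to permanent stop; persistence leads to restart | None in the section | Ordered, but in neither branch |

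Only 6.6.3 restarts because symptoms have not resolved.

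**Step 2. Apply 6.6.3 to each possible state after the hold.**

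- Symptoms resolved, test normal: permanent stop.
- Symptoms resolved, test abnormal: permanent stop.
- Symptoms persist, test normal: restart at 500 mg once daily.
- Symptoms persist, test abnormal: restart at 500 mg once daily.
- No symptoms at any time, test abnormal: no branch applies.

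The test result changes none of the outcomes. The fourth state would include persisting abdominal pain with a raised lipase below Grade IV. The fifth is a realistic case: the kidney item in 6.6.3 names no symptom, and Protocol 7.1.2 requires a laboratory abnormality that leads to drug interruption to be recorded as an AE.

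**Step 3. Does another section supply the causality condition?** Protocol 6.7 lists 6.6.1, 6.6.2 and 6.6.3 as the places where stopping criteria are described, and says the DSMB assesses causality whenever they are met. Protocol 6.6.5 lists the same three sections. On their face, these references bring 6.6.3 under DSMB causality assessment. Their numbering is doubtful, however:

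- 6.6.1 refers to a patient who "meets liver injury criteria as listed in section 6.6.3., the study drug should be interrupted". The liver criteria are now in 6.6.4.
- 6.7 points to 6.6.4 for the DSMB's decision. The DSMB section is now 6.6.5.

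Both are one section too low, so 6.6.3 in these lists may mean the liver criteria. Whichever is meant, 6.6.3 does not make either branch wait for an assessment. The hold lasts 3 days, and the only review interval stated in 6.6.5 is every 3 months.

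**Step 4. Can the direction be settled?** For a swap: 6.6.1, and 6.7 for intercurrent illness, restart only after recovery. A reduced dose with a step-up also suits a recovered patient better than one whose symptoms are thought to have another cause. For a deliberate rule: Protocol 7.2.2 makes abatement after stopping the drug part of its definition of *related*. On that logic, clearing during the hold implicates NTZ and persistence points elsewhere. 6.6.3 states neither rationale.

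**The case against.** The strongest defence is that 6.6.3 is a dechallenge rule. Read with 7.2.2, stopping when symptoms clear off drug and cautiously restarting when they do not is coherent. 6.6.1 governs Grade IV and liver events, so a different rule for milder tolerability problems need not be a drafting error. This stands. A reader might infer that the branches were transposed, but the documents do not prove it.

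A reader might also infer that no causality assessment exists. That goes too far. 7.2.2 requires the investigator to record causality for each AE and to judge laboratory changes, and 6.7 and 6.6.5 both name 6.6.3 for DSMB assessment. What is missing is a link: neither 6.6.3 branch depends on these judgements.

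Finally, a reader might infer that the protocol forces re-dosing through pancreatitis. It does not. Entry to dose adjustment is discretionary. Under 6.7 the investigator may stop NTZ at discretion and must stop it for unacceptable toxicity or toxicity judged against the subject's interest. The amylase, lipase and eGFR tests also have a stated diagnostic purpose. These safeguards limit the harm, but they rest on judgement and are not tied to the ordered tests, so a raised lipase or a fallen eGFR triggers no defined action in 6.6.3.

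**Conclusion.** The point holds on the wording. After the hold, symptoms are the only decision variable. Resolution leads to a permanent stop and persistence to a restart, opposite to the use of resolution in 6.6.1. The ordered tests affect neither branch, laboratory-only events have no branch, and 6.6.3 contains no causality condition of its own. Confidence in these statements is high.

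Whether the branches are reversed or a dechallenge rule was intended remains open, and only the sponsor can say. The laboratory and causality gaps need closing in either case.

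No numerical size is given. The documents state neither how many patients may enter a hold nor how many would recover within 3 days. The conclusion assumes that sites follow 6.6.3 as written and that the DSMB charter, which is not among the documents, does not already supply the missing conditions. This should be corrected, but the stopping powers in 6.7 keep it from being an unguarded hazard.

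**What to change.** Amend Protocol 6.6.3 and the related references as follows.

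1. **Direction.** The sponsor confirms what was intended. If the branches are reversed, swap them. If a dechallenge rule was intended, say so in the text.
2. **Laboratory condition, under either direction.** Do not restart NTZ until the ordered test (amylase and lipase, eGFR, or CK) has been reviewed. Any clinically significant abnormality must have resolved or gone back to baseline, as judged by the investigator against the ULN where one applies and the Day 1 value. All of these tests are already in the Day 1 biochemistry panel in Table 2. Judge laboratory-only events on the same value.
3. **Causality condition.** If NTZ is to be restarted while symptoms persist, first require a documented investigator judgement of *not related* or *unlikely related*, in the terms of 7.2.2.
4. **References.** Correct the section numbers in 6.6.1, 6.7 and 6.6.5, so that it is clear whether DSMB causality assessment covers the dose-adjustment hold, the liver criteria now in 6.6.4, or both.

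The cost is an amended paragraph with corrected references and IRB approval, a repeat blood test when the first result is abnormal, and some holds that run beyond 3 days while a result or judgement is awaited.

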6.6.4. Specific Liver Function Monitoring after Start of Treatment

Liver function monitoring guidelines are detailed below. The cases will be reviewed by the DSMB, who will assess potential Drug Induced Liver Injury (DILI), and apply discontinuation rules as described in 6.6.1., 6.6.2., and in this section.

Study drug interruption

Study drug must be interrupted in the following cases:

- ALT >8x ULN (if ALT is normal at baseline)
- ALT > 5x Baseline (if ALT is elevated at baseline) OR ALT>500 U/L
- ALT >5x ULN (if ALT is normal at baseline) AND Total Bilirubin>2xULN
- ALT >3x Baseline (if ALT is elevated at baseline) OR ALT>300 U/L AND total bilirubin>2xULN
- ALT >5x ULN (if ALT is normal at baseline) AND liver-associated symptoms
- ALT >3x Baseline (if ALT is elevated at baseline) OR ALT>300 U/L AND liver-associated symptoms

In all these cases, close monitoring should be initiated, with repeat liver biochemistries within 24-72 hours. Continue monitoring twice/week until liver biochemistries resolve, stabilize, or return within baseline values. If abnormalities stabilize and patient is asymptomatic, then monitoring should be performed once a week. History of symptoms, disease, concomitant medication, or other conditions such as alcohol consumption or alcohol hepatitis should be obtained for competing etiologies. The cases will be reviewed by the DSMB, who will

determine if the patient may restart study drug (if causality assessment is deemed to be not related to study drug).

Management of liver biochemistries elevations

In the following cases of liver enzyme increase, liver biochemistries including ALT, AST, Total bilirubin, ALP, should be repeated within 2-5 days. Follow up of symptoms should be carefully monitored. Frequency of monitoring should continue once/week until liver abnormalities resolve, stabilize, or return to values below the thresholds mentioned below:

- ALT >5x ULN (if ALT is normal at baseline)
- ALT >3x Baseline (if ALT is elevated at baseline) OR ALT >300 U/L

NOTE: Laboratory assessments should be done centrally. If the patient lives remotely, he/she can have laboratory tests performed locally, and the results communicated to the investigator promptly.

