6.7. Assessment for Premature Discontinuation from Study

Study medication may be discontinued in the following instances:

- Intercurrent illness that would, in the judgment of the investigator, affect assessments of clinical status to a significant degree. Following resolution of intercurrent illness, the subject may resume study dosing at the discretion of the investigator.
- Subject noncompliance
- Investigator discretion
- Study medication must be discontinued in the following instances:
 - Unacceptable toxicity, or toxicity that, in the judgment of the investigator, compromises the ability to continue study-specific procedures or is considered to not be in the subject's best interest
 - Subject request to discontinue for any reason
 - Pregnancy
 - Discontinuation of the study at the request of a regulatory agency or an institutional review board or independent ethics committee (IRB/IEC)

Pre-specified stopping criteria are defined at the patient level and at the study level. These are described in the following sections 6.6.1., 6.6.2., and 6.6.3. In all cases, when the stopping criteria are met, the Data Safety Monitoring Board will perform causality assessment, and decide whether the study drug/study trial may be continued (See section 6.6.4.).

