7.3.4. Follow-up

The Investigator should take all appropriate measures to ensure the safety of the patients, notably he/she should follow up the outcome of any AE until the return to normal or until stabilization of the patient's condition.

The patient must be followed up until clinical recovery is complete and laboratory results have returned to normal, or until progression has been stabilized. This information should be documented in the patient's medical records.

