3.5.2 Clinical Laboratory Tests

Blood and urine samples for chemistry, hematology, coagulation, urinalysis, and other safety markers will be processed by a central laboratory. Values and observed changes from baseline will be summarized at each scheduled visit (Visit 2 Week 4, Visit 3 Week 8, Visit 4 Week 12, Visit 5 Week 16, Visit 6 Week 20, Visit 10 Week 24/Early Termination, and EOS Week 28) by laboratory test based on the Safety Analysis Set.

Shift tables from baseline to maximum post-baseline value (including consideration of unscheduled visits) will be presented for ALT and AST ($\leq 1x$ upper limit of normal [ULN]),

>1xULN to ≤3xULN, >3xULN to ≤5xULN, >5xULN), CK (≤1xULN, >1xULN to ≤2.5xULN, >2.5xULN to ≤5xULN, >5xULN), and total bilirubin (≤1xULN, >1xULN to ≤1.5xULN, >1.5xULN to ≤2xULN, >2xULN).

3.5.3 *Vital Signs*

Values and observed changes from baseline will be summarized at baseline and each scheduled visit (Visit 4 Week 12, Visit 10 Week 24/Early Termination, and EOS Week 28) for vital signs (systolic blood pressure, diastolic blood pressure, and heart rate), weight, and BMI based on the Safety Analysis Set.

3.5.4 *Electrocardiograms*

Values at baseline and Visit 10 Week 24/Early Termination, including the observed change from baseline, for 12-lead ECG parameters (heart rate, PR interval, QRS duration, QT interval, QTc interval, QTcF interval, and RR interval) will be summarized based on the Safety Analysis Set. The overall interpretations (normal, abnormal not clinically significant, or abnormal clinically significant) will be summarized by visit.

3.5.5 *Physical Examinations*

Physical examination findings (normal, abnormal not clinically significant, or abnormal clinically significant) at baseline, Visit 4 Week 12, Visit 10 Week 24/Early Termination, and EOS Week 28 will be summarized by body system based on the Safety Analysis Set.

3.5.6 *Other Safety Assessments*

Other safety assessments such as pregnancy tests will be listed.

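### Protocol 6.6.4 sets a higher ALT limit for a normal baseline than for a baseline of 1-1.67x ULN, and gives normal-baseline patients no trigger at ALT 3-5x ULN even with bilirubin >2x ULN or liver symptoms

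*Protocol*

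**What the plan says.** Protocol 6.6.4 has two tiers.

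**Mandatory interruption**, with repeat labs within 24-72 hours and DSMB review of the case. Four of its six lines combine ALT with a second sign:
- Bilirubin, normal baseline: "ALT >5x ULN (if ALT is normal at baseline) AND Total Bilirubin>2xULN".
- Bilirubin, elevated baseline: "ALT >3x Baseline (if ALT is elevated at baseline) OR ALT>300 U/L AND total bilirubin>2xULN".
- Symptoms, normal baseline: "ALT >5x ULN (if ALT is normal at baseline) AND liver-associated symptoms".
- Symptoms, elevated baseline: the ALT part is "ALT >3x Baseline (if ALT is elevated at baseline) OR ALT>300 U/L", with symptoms added.

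The other two lines use ALT alone: 8x ULN for a normal baseline, and 5x baseline or 500 U/L for an elevated one.

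**Repeat labs within 2-5 days.** The limits are 5x ULN for a normal baseline, and 3x baseline or 300 U/L for an elevated one.

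The patient-level rule in 6.6.1 borrows these limits: a patient who "meets liver injury criteria as listed in section 6.6.3., the study drug should be interrupted". The criteria it means are in 6.6.4, not 6.6.3.

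Protocol 8.3 puts baseline at Day 1 before dosing, and SAP 3.1.3 generally agrees. Section 4.3 excludes ALT or AST above 5x ULN, and section 4.2 sets no minimum ALT. Patients with normal or mildly raised ALT can therefore enrol.

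**The concern.** A baseline-adjusted limit normally allows a patient who starts high to reach a higher ALT before drug is stopped. Here the limit drops as baseline crosses ULN. The patient with the cleaner starting value must reach a higher ALT, and show a larger fold rise, before 6.6.4 requires any action.

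The repeat-lab tier does not help, because for a normal baseline it starts at the same 5x ULN as the combined interruption lines. A normal-baseline patient whose ALT has risen to 3-5x ULN with bilirubin above 2x ULN, or with liver symptoms, falls below both tiers.

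Safety is the primary objective, there is no control arm, and section 1.3 calls this the first study of the drug in this population. The purpose of 6.6.4 is to give possible drug-induced liver injury a fixed response. In this band it gives none to patients who started normal.

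**Working it through.** **Inputs.** From 6.6.4: multipliers 5 (of ULN) and 3 (of baseline), and 300 U/L; for ALT alone, 8, 5 and 500 U/L. From 8.3: baseline is Day 1 pre-dose.

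**Assumptions.** Elevated means above ULN, which the protocol does not define. Each OR pair is bracketed before the AND. The documents give no ALT ULN, so it is varied.

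**Limit in the combined lines**, with b = baseline ALT / ULN:
- b ≤ 1: 5 × ULN
- b > 1: the smaller of 3 × b × ULN and 300 U/L

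**Crossing point.** 3b = 5 gives b = 5/3 = 1.67. For 1 < b < 1.67 the elevated-baseline limit is the lower one. The 300 U/L limit does not affect this while 5 × ULN ≤ 300, that is ULN ≤ 60 U/L.

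**Size of the drop** when baseline goes from ULN to 1 U/L above it:

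| Assumed ULN | Limit at b = 1 | Limit 1 U/L higher |
|---|---|---|
| 30 | 5 × 30 = 150 | 3 × 31 = 93 |
| 40 | 5 × 40 = 200 | 3 × 41 = 123 |
| 55 | 5 × 55 = 275 | 3 × 56 = 168 |

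**Same on-treatment values, three baselines.** ULN 40, ALT 160 (4x ULN), bilirubin 2.5x ULN:

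| Baseline ALT | Fold rise | Limit | 6.6.4 action |
|---|---|---|---|
| 38 | 160/38 = 4.2 | 200 | none |
| 42 | 160/42 = 3.8 | 3 × 42 = 126 | interrupt |
| 60 | 160/60 = 2.7 | 3 × 60 = 180 | none |

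The patient with the largest fold rise gets no action. In general, at on-treatment ALT of k × ULN (3 < k ≤ 5) with the second sign present, the rule interrupts only baselines between 1x and k/3 x ULN: up to 1.17x for k = 3.5, 1.33x for k = 4 and 1.5x for k = 4.5.

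**If ULN exceeds 60 U/L.** Suppose the 300 U/L limit covers all patients. At ULN 70 the normal-baseline limit becomes 300/70 = 4.29x ULN and the inversion ends at 300/(3 × 70) = 1.43x ULN. At ULN 80 the figures are 3.75x and 1.25x. The gap narrows but stays. If 300 U/L covers only elevated baselines, the inversion widens: at ULN 70 a normal baseline has 5 × 70 = 350 U/L, and no elevated baseline exceeds 300.

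**Other bracketing.** If the AND bound only the second half of each OR pair, 3x baseline alone would force interruption and the 5x-baseline line would be redundant. The elevated-baseline limit would be stricter still, so the inversion remains.

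**ALT alone.** 5b = 8 gives b = 1.6, so this tier is inverted below 1.6x ULN.

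**Proposed limit.** The smaller of 3 × max(ULN, baseline) and 300 U/L. At ULN 40 this is 120 at any normal baseline, 123 at 41 and 180 at 60, so it never falls as baseline rises.

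**The case against.** **Other safeguards exist.** A reader might infer that a patient in the gap is unprotected, or that the plan tells the investigator to keep dosing. The documents support neither.
- Liver chemistry is scheduled every four weeks (Table 2). Unscheduled safety visits (6.5.3) and retesting (6.8.3) are available.
- Section 6.7 requires discontinuation for "Unacceptable toxicity, or toxicity that, in the judgment of the investigator, compromises the ability to continue study-specific procedures".
- The DSMB, three liver experts, reviews safety every three months (6.6.5).
- Sections 6.6.1 and 6.6.2 act on CTCAE grades. The documents do not give the laboratory cut-offs for those grades, so one cannot say that no numeric rule anywhere reaches this band.

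This narrows the point to 6.6.4. These safeguards are periodic, rest on judgment or on grade, or count events across patients. None is stated as an ALT limit for one patient in this band.

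**Baseline may not be one reading.** The protocol also calls the screening repeats baseline labs, so a clinician might judge normality on several values. The step of 1 U/L depends on a single Day 1 value; the inversion does not.

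**Elevated-baseline patients are not all caught either.** True: the patient with baseline 60 in the example gets no action now or after the fix. A reader might infer that 4x ULN with raised bilirubin should always stop drug. The elevated-baseline rule is deliberately relative to baseline, and nothing in the documents shows that choice to be wrong.

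**The 3x multiplier is a clinical choice.** Also true. The section uses 3x for elevated baselines only, and no document shows 5x ULN to be wrong in itself. What cannot be defended without a stated reason is a limit that falls as baseline rises.

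**Conclusion.** The point holds for 6.6.4. In the combined interruption lines and the repeat-lab tier, the U/L limit is higher at a normal baseline than at any baseline between 1x and 1.67x ULN. A normal-baseline patient at ALT 3-5x ULN with bilirubin above 2x ULN or liver symptoms meets no trigger there for interruption, early repeat labs or DSMB case review. Section 6.6.1 inherits the gap because it takes its liver criteria from this list.

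This rests on elevated meaning above ULN, the OR pairs being bracketed first, and ULN of at most 60 U/L. Above 60 U/L the result changes in extent, as shown, but does not disappear at the values checked.

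The number of patients affected cannot be derived: the documents give no ULN, ALT distribution or event rate. Assuming log-normal ALT with median 40-60 U/L and log SD 0.5, within-patient CV 10-30% and ULN 30-55, the simulated share with a normal Day 1 ALT runs from about 9% to about 74%. That range is too wide to size the problem. It shows only that such patients may be few or most of the 20.

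**What to change.** Replace the four combined lines in 6.6.4 with one bracketed rule: *interrupt if (ALT >3x the larger of ULN and baseline ALT, or ALT >300 U/L) AND (total bilirubin >2x ULN OR liver-associated symptoms)*. Use the same ALT limit for the 2-5 day repeat-lab tier. In addition:
- State in 6.6.4 that baseline is the Day 1 pre-dose value.
- For known Gilbert patients, who may enrol under 4.3, judge the bilirubin part on direct bilirubin, which is already measured, or on a rise from their own baseline. Otherwise their usual bilirubin might meet that part, leaving ALT >3x ULN to force interruption by itself.
- Correct the pointer in 6.6.1 from 6.6.3 to 6.6.4.
- Ask the clinicians to align the ALT-alone tier, for example at >5x the larger of ULN and baseline or >500 U/L, or to state why 8x ULN is kept.

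The combined and repeat-lab limits for elevated baselines do not change, so many of those patients at ALT 3-5x ULN will still not be interrupted.

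The cost is rewording, with no new scheduled visits or samples. Normal-baseline patients will have some more repeat labs and reversible interruptions. Under the simulation assumptions above, with no true rise, at most about 1.6% of them would exceed 3x ULN at any of six on-treatment visits. The number with true rises cannot be derived from the documents.
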